The individual subject will be participating in the study for approximately 1-8 hours depending on how long the procedure takes. We will then follow-up their delivery information using labor and deliveries' EMR (Peribirth). The patient will not be contacted at this time. Once delivered they will no longer be part of the study. Delivery usually occurs within 5 weeks of the procedure given that the procedure is only done at 37 weeks or higher.

Duration Anticipated to Enroll All Study Subjects

We will be enrolling study subjects for 2 years.

Estimated Date for the Investigators to Complete This Study Within two years

Procedures for Subjects to Request Withdrawal

Patients can withdraw at anytime and will be aware of that option. We will be conducting an intention-to-treat analysis. If the patient decides to withdraw we will then ask the patient if we can still collect their demographic and delivery data. If they allow this, then they will be included in the analysis and this will be stated in our results once the study is written. No identifiers will be included in the results. If they would like to withdraw completely we will not collect any further data and we will not include them in our analysis.

Procedures for Investigator to Withdraw Subjects

There is no circumstance that the patient will be withdrawn without their consent. There is no anticipated reason that a patient would need to be terminated from the study. If there is any concern that there is risk to the fetus during the procedure, the procedure will be terminated and the patient will still be included in the study. This will then be discussed and explained in our study results.

Participants Will Be Recruited Yes
Recruitment Method(s) Clinical Practice

How Participants Will Be Identified

Each day external cephalic versions are scheduled on labor and delivery. When a patient is noted to be scheduled for a version, once they are admitted and there is no contraindication noted for the participation in the study (for example, they come for a version but are found to be in the cephalic presentation that day) they will be asked if they are willing to participate in a study. If the patient agrees, a member of the research team will approach the patient and discuss the study with the patient.

Who Will Initially Approach Potential Participants Study Personnel

How Research Will Be Introduced to Participants

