Description of the Source Records that Will Be Used to Collect Data About Subjects

In order to collect data about the procedure, a member of the research team will fill out a questionnaire at the time of procedure and all questionnaires will be placed in a locked cabinet in the PI's office in Mount Sinai West- Suite-10C. All other data about delivery and demographics will be collected after the procedure using labor and deliveries' electronic medical record system (Peribirth).

Description of Data that Will Be Collected Including Long-Term Follow-Up

Protected Health Information (PHI) will be collected and used in the study. No PHI will be disclosed. Only study personnel will have access to subject information. The study investigators will collect medical information about the subject over the course of the study. Study data will be entered into a de-identified research secure password-protected database, using a unique code numbering system. A code number linked to subject identity will be used instead of names. The code number will not be derived from any patient identifiers, such as patient name or medical record number. The record linking the subjects' name with their assigned codes will be kept on a password protected file on a secure departmental drive. Only the PI will have access to this file. All study forms will be kept private and stored in a locked file cabinet in a secure location in the office of the PI. The secure computerized research database will be on a password-protected file within the OB/GYN department at Mount Sinai West. The linked code and dates of service are the only patient identifiers to be collected onto the computerized database spreadsheet along with the subject's medical information needed for the purposes of the study. Once data collection and analysis is completed, the linked code and data will be deleted.

Research Requires HIV Testing

13. Procedures - Genetic Testing

Genetic Testing Will Be Performed No

14. Procedures - Details**Surveys or Interviews** Yes**Type of Instruments Being Used** Created By Research Team**Description of Instruments Created By Research Team**

The research team has created a questionnaire that will be filled out by the person performing the procedure once the procedure is completed. This questionnaire will then be collected by the PI and stored in a locked cabinet in the PI's office.

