Accessing Data Yes

Receipt or Transmission of Data Yes

Holding Code That Can Be Linked to Identity of Participants No

Research Personnel Responsible for: [name]

Accessing Data Yes

Receipt or Transmission of Data Yes

Holding Code That Can Be Linked to Identity of Participants No

Research Personnel Responsible for: [name]

Accessing Data Yes

Receipt or Transmission of Data Yes

Holding Code That Can Be Linked to Identity of Participants No

Research Personnel Responsible for: [name]

Accessing Data Yes

Receipt or Transmission of Data Yes

Holding Code That Can Be Linked to Identity of Participants No

Research Personnel Responsible for: [name]

Accessing Data Yes

Receipt or Transmission of Data Yes

Holding Code That Can Be Linked to Identity of Participants No

Research Personnel Responsible for: [name]

Accessing Data Yes

Receipt or Transmission of Data Yes

Holding Code That Can Be Linked to Identity of Participants No

Research Personnel Responsible for: [name]

Accessing Data	Yes
Receipt or Transmission of Data	Yes
Holding Code That Can Be Linked to Identity of Participants	No

Duration Data Will Be Stored

Data will be stored until the data is analyzed, within 1 year from study completion.

Steps That Will Be Taken to Secure the Data During Storage, Use, and Transmission

The study investigators will collect medical information about the subject over the course of the study. Study data will be entered into a de-identified research database, using a unique code numbering system. A code number linked to subject identity will be used instead of names. The code number will not be derived from any patient identifiers, such as patient name or medical record number. The record linking the subjects' name with their assigned codes will be kept on the computer in a separate secure folder. All files are password protected on a secure server.

Data Analysis Plan Including Any Statistical Procedures

Continuous variables will be analyzed using two tailed T-test and categorical variables will be analyzed using Pearson Chi Square test. Logistic regression will be used to adjust for confounders. A p-value <0.05 will be considered significant.

22. Data - Safety Monitoring

More Than the Minimum Data Safety Monitoring Will Be Done No

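### The plan promises intention-to-treat but drops randomised patients who withdraw completely, including any version result already recorded

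*Combined protocol and SAP*

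**What the plan says.** The rules are in section 9 (Subjects - Participation), under Procedures for Subjects to Request Withdrawal. The analysis principle is "We will be conducting an intention-to-treat analysis", and on timing, "Patients can withdraw at anytime and will be aware of that option". Patients who withdraw are then split in two:

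- **Partial withdrawal.** On withdrawal, "we will then ask the patient if we can still collect their demographic and delivery data". For those who agree, "If they allow this, then they will be included in the analysis".
- **Complete withdrawal.** "If they would like to withdraw completely we will not collect any further data and we will not include them in our analysis".

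The next paragraph, on withdrawal by the investigator, covers a version stopped for fetal risk: "the procedure will be terminated and the patient will still be included in the study". Stopping the procedure is therefore not withdrawal, and those patients are unaffected.

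Section 12, on source records, says that "a member of the research team will fill out a questionnaire at the time of procedure". Section 14 adds that the operator completes the form after the procedure. The data analysis plan in section 21 gives the tests ("categorical variables will be analyzed using Pearson Chi Square test"), logistic regression for confounders and a 0.05 threshold. It says nothing about analysis sets, unknown outcomes or sensitivity analyses.

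**The concern.** Intention-to-treat keeps every randomised patient in the group to which she was assigned. The complete-withdrawal rule takes some of them out. It also joins two separate decisions in one sentence: to stop collecting data, which respects the patient's wish, and to leave the patient out of the analysis, which also discards what is already held.

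Exclusion after randomisation matters when it depends on both arm and outcome. No blinding is described, and the primary outcome is known within hours. A patient may therefore know her arm and her result when she decides to withdraw. If that decision depends on both, the comparison of success rates is biased, in a direction the documents do not settle. The stated objective is to test whether the two strategies have the same success rate, so a bias that hides a real difference matters at least as much as one that creates a false one.

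**Working it through.** **1. Can the rule reach a patient with a recorded primary outcome?** Section 12 (study design) places randomisation directly after consent. Section 9 allows withdrawal at any time and follows patients by chart to delivery, usually within 5 weeks of the procedure. The version result is on the questionnaire from the day of the procedure. A patient can therefore withdraw completely with her primary outcome on file. The text does not say in so many words that this result is discarded. It follows because the limit to further data applies only to collection, the exclusion from analysis has no exception, and nothing elsewhere keeps the result.

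**2. Inputs for a sense of scale.** The documents give 100 patients in total, a Pearson chi-square test and a 0.05 threshold. They give no expected success rates, allocation ratio, power or withdrawal rate, so the sample size cannot be reproduced. Assumptions: 50 per arm, true success *p* of 50%, 60% or 70%, and no continuity correction. Rejection rates come from exact enumeration.

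**3. One failure removed from one arm.** The shift is 50*p*/49 − *p*:
- *p* = 0.5: 25/49 − 0.50 = +1.0 point
- *p* = 0.6: 30/49 − 0.60 = +1.2 points
- *p* = 0.7: 35/49 − 0.70 = +1.4 points

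**4. Equal true rates, each failure in one arm only lost with probability *q*.** Expected losses are 50(1 − *p*)*q*. The bias in that arm is *p*/[*p* + (1 − *p*)(1 − *q*)] − *p*. For example, at *p* = 0.6 and *q* = 0.1 it is 0.6/0.96 − 0.6 = 2.5 points.

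| *q* | Expected failures lost (*p* = 0.5 / 0.6 / 0.7) | Bias, points | Rejection rate |
|---|---|---|---|
| 0 | 0 | 0 | 0.0569 / 0.0524 / 0.0498 |
| 0.05 | 1.25 / 1.0 / 0.75 | 1.28 / 1.22 / 1.07 | 0.0527 / 0.0529 / 0.0524 |
| 0.10 | 2.5 / 2.0 / 1.5 | 2.63 / 2.50 / 2.16 | 0.0578 / 0.0583 / 0.0576 |
| 0.20 | 5 / 4 / 3 | 5.56 / 5.22 / 4.47 | 0.0848 / 0.0829 / 0.0789 |

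**5. Patterns that do little harm to the false-positive rate.** With failures lost equally from both arms, the rejection rate is 0.0505 / 0.0510 / 0.0510 at 10% and 0.0513 / 0.0509 / 0.0509 at 20%. With one arm losing patients regardless of outcome, it is 0.0506 / 0.0512 / 0.0512 at 10% and 0.0513 / 0.0514 / 0.0509 at 20%. Both are about 0.051.

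**6. A real difference.** With true success of 70% against 50%, power is 0.55 with no exclusions. Losing 10% of failures changes it to 0.43 if they come from the lower arm only, 0.63 if from the higher arm only, and 0.51 if from both.

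**7. A borderline result.** 35/50 against 26/50 gives p = 0.065. Removing one failure from the higher arm, 35/49 against 26/50, gives p = 0.047. When the result is close, one exclusion can decide which side of 0.05 it falls on.

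**The case against.** The best counter-argument is that hardly anyone will be affected. Active participation lasts about 1-8 hours, and follow-up is by chart without contact, so a patient who withdraws after the version must start the process herself. Those who agree to data use stay in, stopped procedures stay in, and the investigator withdraws nobody without consent. The number of complete withdrawals could be zero.

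The numerical harm also needs an extreme pattern. Against the no-exclusion baseline, losing 10% of failures from one arm alone adds only 0.0009, 0.0059 and 0.0078 to the rejection rate at 50%, 60% and 70% success. That is about the size of the test's own discreteness. Clear inflation needs one in five failures lost from one arm and none from the other, and nothing in the documents suggests this.

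The remedy is limited too. A patient who withdraws completely may also refuse use of what has been recorded. What may be kept depends on the consent form and authorisation, which were not available for review. Patients with no usable result still drop out of the primary comparison, and best-case and worst-case bounds are one option among several.

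All of this stands as a limit on size and on what the remedy can recover. None of it reconciles the two statements, and rarity cannot be relied on when the plan gives no expected number.

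**Conclusion.** The concern holds. The plan states an analysis principle and, in the same paragraph, a rule that breaks it; nothing elsewhere repairs the conflict. That conclusion rests on the text alone and needs no assumption.

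The effect on the result is possible rather than likely, and small if complete withdrawals are rare. The figures are illustrations that assume 50 per arm and 50-70% success. On that basis the false-positive rate moves little until something like 10% of failures are lost from one arm only, and clearly at 20%. One-sided loss can also lower or raise apparent power when the arms truly differ. The change should be made, because it is cheap and because who counts in the analysis is best settled before results are known. It is not a fatal flaw.

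**What to change.** In the withdrawal paragraph of section 9, separate stopping collection from discarding data. State that after complete withdrawal nothing more is collected, while data recorded beforehand, including the version result, are kept and analysed in the assigned group where the consent and authorisation permit. Add the version result to the items a withdrawing patient is asked to let the study keep; at present only demographic and delivery data are named.

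In the data analysis plan in section 21:
- Define the intention-to-treat set as all randomised patients by assigned group.
- State that the primary comparison uses all randomised patients with a known version result.
- Treat a result that may not be kept as unknown, and report unknown results by arm.
- Add best-case and worst-case sensitivity analyses. With 50 per arm, each unknown widens its arm's range by 1/50 = 2 points. Two unknowns in each arm give a range of 4/50 = 8 points for the difference.

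This does not recover patients with no usable result. The gain is the recorded results kept, plus open reporting and bounds for the rest. The cost is protocol wording, possibly consent wording, and one sensitivity table.

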The primary outcome will be the success rate of external cephalic version to cephalic presentation. Secondary outcomes will include: time from procedure to delivery, mode of delivery, patient discomfort, adverse events during procedure (ie.fetal bradycardia, emergent cesarean section, abruption), neonatal outcomes (ie. birthweight, Apgars, cord pH, NICU admission). The external cephalic version procedure may be terminated in any patient at any time regardless of this study in the event of persistent fetal heart rate abnormalities, maternal request, or any other adverse findings that the physician believes is an indication that the procedure must be terminated.

Protocol Was Already Approved by the Icahn School of Medicine at Mount Sinai (ISMMS) Institutional Review Board (IRB) Under a Different Principal Investigator No

Protocol Was Previously Submitted to an External(non-ISMMS) IRB No

4. Research Personnel

Name/Department	Role/Status	Contact	Access	Signature Authority	Phone	Email
[name] / Obstetrics/ Gynecology	PI /	Yes	SIGNAUTH			
[name] / Obstetrics/ Gynecology	Co-Investigator /		EDIT			
[name] / Obstetrics/ Gynecology	Co-Investigator /		EDIT			
[name] / Obstetrics/ Gynecology	Co-Investigator /		EDIT			
[name] / Obstetrics/ Gynecology	Co-Investigator /		EDIT			
[name] / Anesthesiology	Co-Investigator /		EDIT			
[name] / Anesthesiology	Co-Investigator /		EDIT			
[name] / Anesthesiology	Co-Investigator /		EDIT			

5. Sites

Site Name Mount Sinai West

Other External Site Name

Contact Details

Approved 0

Approval Document

Funded By Mount Sinai 1

Reviewed By Mount Sinai IRB

Other IRB

6. Subjects - Enrollment

Site Name	Mount Sinai Roosevelt
Subjects To Be Enrolled	
100	
Total	100

7. Subjects - Setting and Resources

Setting of Human Research Other

Specify Other Setting of Human Research

Labor and Delivery unit at Mount Sinai West hospital.

Total Number of Subjects Needed 100
To Complete Study

Feasibility of Meeting Recruitment Goals

From 2012-present we have attempted approximately 89-115 external cephalic versions a year. Each year we have been increasing in numbers, with 115 patients in 2015. These numbers only include patients who had an attempted ECV and does not include patients that were scheduled for ECV but the procedure was not performed for various circumstances. Given this information we believe that it will take approximately 1-2 years to recruit 100 patients.

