Once they are admitted for a version and there are no contraindications for the procedure, the patient will be asked if they are willing to participate in a study. If so, a member of the research team will approach the patient. In a private setting, they will be introduced to the study and will be given as long as they need to decide whether they would like to participate in the study. Since the patient will be receiving IV hydration prior to the procedure (whether or not they are going to be part of the study), they will be given as long as it takes for the IV fluids to run. This is usually between 30 minutes to an hour. If they need more time to decide, they will be given additional time as needed.

How Participants Will Be Screened

Participants will be screened by looking at the scheduling book each day.

10. Subjects - Risk and Benefits

Risks to Subjects

Overall, there is a minimal risk to subjects who participate in this study. In terms of the procedure itself, there have been adverse events reported after ECV including placental abruption, umbilical cord prolapse, rupture of membranes, stillbirth and fetomaternal hemorrhage. These adverse events are rare, occurring in less than 1% and thus the American College of Obstetrics and Gynecology (ACOG) does endorse attempting ECV when possible in centers where prompt evaluation and, if necessary, cesarean delivery is readily available. In regards to neuraxial analgesia, Magro-Malosso et. al, recently performed a meta analysis comparing use of neuraxial analgesia versus controls during ECV attempts and found no difference in adverse outcomes between groups (emergency cesarean delivery, transient bradycardia, nonreassuring fetal testing, or placental abruption). It does appear that patients who do not receive neuraxial analgesia do experience more discomfort during the procedure.

Description of Procedures Taken to Lessen the Probability or Magnitude of Risks

In order to lessen the magnitude of risks, patients will be monitored for at least 30 minutes post procedure as recommended by ACOG, or longer if fetal testing is non-reassuring. In addition, procedure attempts will be terminated if the provider believes there is risk to the fetus at any time. This procedure is also done under ultrasound guidance to monitor the fetus throughout. Lastly, patients will be given strict post procedure precautions for when they are discharged from the hospital.

Provisions for Research Related Harm / Injury

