There is no anticipated research related harm for study subjects. There is a very small risk of adverse outcomes inherent in the procedures themselves, but this is not due to participating in research. Medical personal will be readily available for any adverse outcome as is standard for all pregnant patients in such events.

Expected Direct Benefit to Subjects

Each subject may be expected to directly benefit from participation in this study. For those that are in the immediate spinal group, these patients may benefit from less discomfort (as is noted in prior studies) and an increased external cephalic version success rate (compared to controls). Those who are in the spinal anesthesia only if ECV fails without it, may benefit from not having to undergo an additional procedure (neuraxial anesthesia) when attempt leads to cephalic presentation with ease. It is unclear if these patients will have the same ECV success rate, but prior non-randomized trials do suggest this finding.

Benefit to Society

The results of this study may benefit society in that a better protocol may be in place for ECV attempts that increases the rates of success without increasing the rate of risk or cost.

Provisions to Protect the Privacy Interests of Subjects

The patients will be approached by the a member of the study team on the labor floor to determine if they are willing to be included in the study. Their participation will not require any additional examinations. They will only be approached once by the study team on the labor floor to determine if they are willing to participate. All research-related discussions will be held in the patient's private room. Any questions will be answered and fully discussed to maximize patient comfort. Patients will be allowed time to consider participation and we will explain to patients that we will follow up their delivery information, but will not contact them directly. We will also assure the patient all the steps that will be taken to protect their privacy.

Economic Impact on Subjects

We do not see any foreseeable additional costs to subjects for participating in this research study. The patient is already in the hospital to undergo a version and anesthesia may or may not be used for this procedure even when not participating in the study.

11. Subjects - Pregnant Women

**Preclinical Studies Including Those No
on Pregnant Animals and Clinical
Studies Including Those on Non-
Pregnant Women Have Been
Conducted**

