Data for Assessing Potential Risks to Pregnant Women and Fetuses

There have been many studies on pregnant women undergoing external cephalic versions. These studies have concluded that attempting ECV is beneficial, and use of neuraxial anesthesia also increases success rates and decreases cesarean section rates. They have also found no increased rate of adverse outcomes. Since this procedure is only performed in the third trimester no inducements, monetary or otherwise, will be offered to terminate a pregnancy. Individuals engaged in the research team will have no part in any decisions as to timing, method, or procedures used to terminate a pregnancy. Individuals engaged in the research will have no part in determining the viability of a neonate.

PI must attest that all of the following are true. * No inducements, monetary or otherwise, will be offered to terminate a pregnancy. * Individuals engaged in the research will have no part in any decisions as to the timing, method, or procedures used to terminate a pregnancy. * Individuals engaged in the research will have no part in determining the viability of a neonate.

12. Procedures - Narrative

Description of the Study Design

This is a randomized controlled trial comparing two groups. Patients will be admitted to labor and delivery for external cephalic version. They will be approached by a member of the research team if they are eligible to participate. If they choose to consent, they will be randomized into Group 1 or Group 2. Patients will then undergo the procedure as described below.

Description of Procedures Being Performed

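### Difference tests at p<0.05 in 100 patients cannot support a statement that risk is not increased; report adverse-event risk differences with 95% intervals instead

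*Combined protocol and SAP*

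**What the plan says.** All references are to the combined protocol and SAP.

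- **Section 10, Benefit to Society.** The hoped-for gain is worded as follows: "a better protocol may be in place for ECV attempts that increases the rates of success without increasing the rate of risk or cost". The sentence is conditional, and it sits in a benefit field of the ethics application.
- **Section 3, Primary and Secondary Study Endpoints.** The primary outcome is version success. Secondary outcomes include "adverse events during procedure (ie.fetal bradycardia, emergent cesarean section, abruption" and neonatal outcomes. Section 19 lists several of the neonatal outcomes as binary: low 5-minute Apgar score, low arterial cord pH and NICU admission.
- **Section 21, Data Analysis Plan.** For binary outcomes, "categorical variables will be analyzed using Pearson Chi Square test". Logistic regression is added to adjust for confounders, with no outcome or covariate named. The decision rule is "A p-value <0.05 will be considered significant". No interval, margin or safety hypothesis is given.
- **Section 7, Feasibility of Meeting Recruitment Goals.** The sample size rests on throughput: "Given this information we believe that it will take approximately 1-2 years to recruit 100 patients".
- **Section 12, Description of the Study Design.** Patients who consent are allocated ("they will be randomized into Group 1 or Group 2") with no ratio given.
- **Section 10, Risks to Subjects.** After naming abruption, cord prolapse, rupture of membranes, stillbirth and fetomaternal hemorrhage, the text says "These adverse events are rare, occurring in less than 1" percent.

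**The concern.** A difference test asks whether the data conflict with equal risk. It does not ask how large an increase the data leave open. With few events a p-value above 0.05 is the likely result even when one strategy is materially riskier, and section 21 provides nothing else from which to judge that.

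The exposures differ by design. Every Group 1 patient has a spinal before the attempt. Group 2 patients have one only after a failed attempt, followed by a second attempt. The stated hypothesis is equal success. If success does look similar, the choice between strategies will turn on secondary outcomes, safety among them. A reader could then take a non-significant adverse-event comparison as reassurance that the trial cannot give.

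**Working it through.** **The plan's own figure.** N = 100 cannot be reproduced, because the documents give no power, effect size, event rate or margin. It is a recruitment figure.

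**Inputs.**
- N = 100 (sections 6 and 7).
- Alpha 0.05 (section 21). Two-sided testing is stated only for the t-test and is assumed here for chi-square.
- 50 per arm: assumed 1:1 allocation.
- Base rate 1%: the upper end of the figure in section 10. Of the three adverse events named in section 3, it covers only abruption.
- Base rates 5% and 10%: assumptions. The documents give no rate for fetal bradycardia, emergent cesarean or the neonatal outcomes.

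**Step 1: power of the stated test.** For counts x and y out of 50, and pooled proportion p̄ = (x+y)/100, the uncorrected statistic is X² = (x/50 − y/50)² / [p̄(1−p̄)(2/50)], rejecting above 3.841. Summing the binomial probabilities of every rejecting pair gives exact power:

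| True rates | Power | Chance of missing the difference |
|---|---|---|
| 1% vs 2% | 1.1% | 98.9% |
| 1% vs 5% | 14.9% | 85.1% |
| 1% vs 10% | 53.3% | 46.7% |
| 1% vs 15% | 81.1% | 18.9% |
| 5% vs 10% | 14.5% | 85.5% |
| 5% vs 15% | 39.3% | 60.7% |
| 10% vs 20% | 30.3% | 69.7% |

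For 80% power the worse arm would need about 15% from a base of 1%, 24% from 5%, or 32% from 10%. With 40 per arm, as a sensitivity case, power is 9.6% (1% vs 5%), 14.6% (5% vs 10%) and 24.7% (10% vs 20%). The second figure does not fall because the test is discrete.

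**Step 2: how often there is nothing to test.** At a true 1% rate, the chance of no event in an arm of 50 is 0.99^50 = 0.605. The chance of none in either arm is 0.99^100 = 0.366, and chi-square is then undefined. Logistic regression cannot help with so few events.

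**Step 3: what an interval would show.** The Newcombe interval combines the two Wilson intervals. For 0/50 the Wilson limits are 0 and z²/(n+z²) = 3.841/53.841 = 0.0713. With 0/50 in both arms, the limits for the difference are ±√(0.0713² + 0²) = ±7.1 points. By the same method:
- 1/50 vs 1/50: ±8.7 points.
- 5/50 vs 5/50: ±12.7 points.
- 6/50 vs 1/50: X² = 3.840, just short of 3.841, so not significant; interval −0.6 to +21.9 points. This borderline table is chosen to illustrate the point.

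**Step 4: size needed.** For 80% power, n per arm = [1.960√(2p̄(1−p̄)) + 0.842√(p₁(1−p₁)+p₂(1−p₂))]²/(p₁−p₂)². For 10% vs 20% this is (0.990 + 0.421)²/0.01, or 199 before rounding of the terms. The same formula gives 285 for 1% vs 5% and 435 for 5% vs 10%.

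To exclude an increase of m when both arms have true rate p (one-sided 0.025, 80% power), n per arm = (1.960+0.842)²·2p(1−p)/m². With p = 1% and an illustrative m of 2 points, this is 7.849 × 0.0198/0.0004 = 389. With m = 5 points it is 63. The documents set no margin, and the normal approximation is rough at 1%.

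**The case against.** A reader might infer that the investigators intend to report a non-significant adverse-event test as proof of no added risk. The documents do not say so. Section 21 says what counts as significant and is silent on p above 0.05. Section 3 states a hypothesis about success only. The section 10 sentence is a conditional hope, and it also mentions cost, for which no outcome is listed. It is not a list of what the trial will demonstrate. This objection stands: the risk is of misreading, not of a stated rule.

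A reader might also infer that the trial would miss most harms that matter. That goes too far. The under-1% figure covers only abruption among the named adverse events, every other rate above is assumed, and very large increases would be detected with about 80% power.

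Nor must a safety statement rest on this trial alone. Section 10 cites a meta-analysis finding no difference in adverse outcomes with neuraxial analgesia, and section 11 says the same of prior studies. Section 9 also promises to discuss procedures terminated for fetal risk. These count, but only in part: section 3 says no randomized trial has evaluated neuraxial analgesia reserved for a failed first attempt, which is the strategy compared here.

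Finally, low power for rare secondary outcomes is common in a trial of 100, and authors could report intervals without being told to. Both points are true. They limit the weight of the concern but do not remove the case for specifying the interval in advance.

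**Conclusion.** The concern holds in a limited form. The stated between-arm analyses of binary safety outcomes are difference tests at p<0.05, and at this size a non-significant result could not support a statement that risk is not increased. Power is about 15% for a rise from 1% to 5% or from 5% to 10%, and about 30% for a rise from 10% to 20%. Even a trial with no events leaves a difference of up to 7.1 points in either direction.

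These figures rest on 1:1 allocation, two-sided testing, no loss of patients and, apart from the under-1% figure, assumed event rates. Complete withdrawals, which section 9 removes from the analysis, would generally reduce precision further. This is an inexpensive improvement to the reporting plan. It does not bear on the primary success comparison or on whether chi-square is valid for small counts.

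**What to change.** **Section 21.** Add, for each binary adverse-event and neonatal outcome:

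> The main safety summary will be events/N by arm and the risk difference with a 95% Newcombe (score) confidence interval. Any p-value shown is secondary. The safety conclusion will be drawn from the interval and will state the largest excess risk that it does not exclude.

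The order of precedence is needed because the two methods can disagree in sparse tables. For example, 4/50 vs 0/50 gives X² = 4.17 (p = 0.041), but a Newcombe interval of −0.6 to +18.8 points.

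**Section 10, Benefit to Society.** Replace the clause about not increasing risk with a statement that the trial will describe adverse-event rates under each strategy and is not sized to exclude an increase in risk.

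**Cost.** A few sentences, with no new data, patients or procedures. The intervals will be wide, and the trial gives up any claim of no added risk.
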